1.0 Study Summary

Study Title	Pilot Study of Nurse-Administered Touch and Biobehavioral Stress Responses of Preterm Infants (Pilot NAT-BIO Study)
Study Design	Randomized cross-over clinical trial
Primary Objective	Determine the effect of a nurse-administered touch intervention (NaTI) on biobehavioral stress responses of preterm infants during essential nursing care.
Secondary Objective(s)	(2) Identify factors to increase feasibility of the NaTI as a nurse-administered, integrated part of essential, procedural care, (3) Determine associations between biobehavioral responses and early neurobehavior.
Research Intervention(s)/ Investigational Agent(s)	NaTI (NaTI): NaTI is a systematic touch intervention consisting of 3 static, brief touches lasting a total duration of 2.5 minutes provided by bedside nurses at specified points during essential care. The intervention is provided with bare hands (i.e. gloves are not worn).
IND/IDE #	N/A
Study Population	Preterm infants born 27 to 30 weeks post-menstrual age; NICU nurses
Sample Size	Up to 20 infants; up to 20 nurses
Study Duration for individual participants	Infant participation on each of 2 days will last approximately 6 hours from the attachment of electrodes for skin conductance responses and heart rate/heart rate variability to the removal of these electrodes. Infant participation will include data collection on two consecutive days for a total duration of 24-48 hours. Infant neurobehavior will be assessed at 35 weeks post-menstrual age. The assessment takes 20-30 minutes. Total infant participation will last from the time of the first observation to neurobehavioral assessment (approximately 5-7 weeks), depending on anticipated discharge and clinical stability for the neurobehavioral assessment. Nurse participation will last approximately 15 minutes per survey completion.
Study Specific Abbreviations/ Definitions	NaTI: nurse-administered touch intervention SC: standard care NAPI: Neurobehavioral Assessment of the Preterm Infant AIM: Acceptability of Intervention Measure IAM: Intervention Appropriateness Measure FIM: Feasibility of Intervention Measure SID: study-specific identification Observation period: period of active study participation for infants lasting approximately 6 hours and beginning with the attachment of electrodes before the scheduled care episode during which data collection will occur and ending with the following scheduled care episode when electrodes are removed.

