Essential nursing care activates the sympathomedullary (SAM) pathway and hypothalamic-pituitary-adrenal (HPA) axis, resulting in measurable biobehavioral effects^{2,19-22}. SAM pathway activation increases sympathetic nervous system (SNS) activity and suppresses parasympathetic nervous system (PNS) activity in response to painful procedures^{23,24} and essential nursing care^{21,22,25,26}. Stress responses resulting from SAM pathway activation can be measured as changes in vital signs (heart rate [HR], respiratory rate [RR], oxygen saturation [SpO2])²⁷, HRV²⁷, and SCRs²⁴. The release of catecholamines from the adrenal medulla in response to SNS stimulation²⁸ causes stimulation of the cardiac sinoatrial node and measurable changes in HR, RR, SpO2, and HRV²⁷. HRV represents the beat-to-beat variations in HR, as measured by the R-R interval, and is sensitive to inputs from the SNS and PNS^{29,30}. SCRs, produced by the filling and emptying of palmar and plantar sweat glands in response to SNS stimulation²⁴, are valid measures of SAM pathway activation in

the first weeks of life in infants born <34 weeks post-menstrual age (**PMA**)³¹. Further, activation of the HPA axis causes a release of cortisol from the adrenal cortex²⁸. Cortisol can be quantified from saliva²⁸, providing a non-invasive measure that is highly correlated with blood levels^{32,33}. Salivary cortisol levels increase in preterm infants in response to bathing²⁶, routine handling³⁴, and painful procedures³⁴ and decrease in response to pain management interventions³⁴. Early, repeated activation of the immature SAM pathway and HPA axis during essential caregiving may cause aberrant changes in the form of neural programming of these stress response systems, altering their function and contributing to NDI³⁵. Neonatal HRV, for example, is associated with childhood neurodevelopment^{36,37} and may be an important end-point for powering future studies. Thus, we will determine associations between HRV, as well as HR, SCRs, and cortisol, and infant neurobehavior at 35 weeks PMA.

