4.0 Study Endpoints

- 4.1 Data collection to accomplish aims 1 & 2 will last the duration of two observation periods, one each on two consecutive days. Infant participation will last approximately six hours for each observation period. Participation will begin approximately three hours prior to a scheduled care episode (i.e. data collection period) when monitoring electrodes are attached and will end approximately 2.5 hours after the scheduled care episode (i.e. data collection period) when the next care episode begins and study electrodes are removed. Infants will receive a neurobehavioral assessment at approximately 35 weeks PMA. The timing of this assessment will depend on anticipated discharge and clinical stability. Infant participation for the entire study will last between 5-7 weeks, depending on infant PMA at birth and timing of the neurobehavioral assessment.
- 4.2 The NaTI will be stopped for infants experiencing bradycardia, defined as HR less than 100 beats per minute for 10 seconds, or oxygen desaturation, defined as oxygen saturation less than 85% for 10 seconds. To prevent the overstimulation of infants during intervention delivery, the NaTI will be stopped for tachycardia, defined as HR greater than 200 beats per minute for 10 seconds. NaTI delivery may resume with the next planned intervention point in the care but will be discontinued for the remainder of the care for two or more episodes of bradycardia, oxygen desaturation, or tachycardia occurring during intervention delivery as defined above. A few infants may not tolerate the handling required to complete the neurobehavioral assessment. The Neurobehavioral Assessment of the Preterm Infant (**NAPI**) is intended to be administered in a specified, fixed sequence to minimize infant handling and potential distress. While we expect that infants at 35 weeks PMA will not find the assessment distressing, for those who exhibit signs of distress (e.g. bradycardia, oxygen desaturation, inconsolable crying), the assessment will be terminated.

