6.2 **Procedures. Aims 1.** Infants will be enrolled during the first 10 days of life. We will collect demographic and clinical data from the infant's electronic health record (**EHR**) after enrollment and throughout the hospitalization. Because stress responses may differ based on postnatal age⁸¹, data collection for stress responses will occur between 10 and 20 days of life. To eliminate variance in cortisol due to diurnal patterns, we will perform all observations at the same time of day for all infants, between 1000 and 1300. Observations will occur on two consecutive days unless infants are not available due to off-unit or other scheduled procedures. In this case, the second observation will occur on the next day that the infant is available. Infants will be assigned to receive standard care or standard care with a NaTI in a randomly assigned sequence. For the two observed care episodes, we will require that nurses provide this care exclusively to limit confounding by the participation of additional caregivers. With assistance from the bedside nurse, the researcher, who is a Registered Nurse, will attach monitoring electrodes for vital signs, HRV, and SCRs during the care episode prior to the observed care to minimize stress responses from handling and monitoring prior to the baseline period (Fig 2). Nurses commonly attach monitoring electrodes as part of their clinical practice.

[figure not shown]

Figure 2. Timeline of study measures.

Measures, Aims 1:

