- **Demographic questionnaire.** This questionnaire will include baseline data on participating nurses such as age, sex, race, nursing education, and nursing experience.

- ***NaTI survey.*** This investigator-developed survey uses Likert-style ratings and open-ended questions to evaluate nurses' experiences, attitudes, perceptions, and suggested improvements for the NaTI.
- ***Acceptability, appropriateness, and feasibility measures.*** Nurses will complete the Acceptability of Intervention Measure (**AIM**), Intervention Appropriateness Measure (**IAM**), and Feasibility of Intervention Measure (**FIM**)⁹⁰. Each measure includes four Likert-style questions evaluating the degree to which respondents like the intervention, find the intervention useful, and believe that the intervention can be practically implemented.
- ***Preliminary cost.*** We will estimate preliminary cost of the intervention as part of the feasibility assessment using the nursing time required to deliver the intervention and nursing time and interventions required to respond to infant physiologic instability during the recovery period.

Procedures. Aim 3. At approximately 35 weeks PMA, we will administer the NAPI to each enrolled infant. If discharge is anticipated prior to 35 weeks PMA, we will coordinate with clinical staff to perform the assessment prior to the infant's discharge. For infants who are not clinically stable based on nursing judgment or are requiring invasive ventilation or continuous positive airway pressure (**CPAP**) at 35 weeks PMA, we will delay the neurobehavioral assessment until the infant is clinically stable. Neurobehavioral assessments will be coordinated with the clinical staff so as not to interfere with clinical operations and will occur prior to a scheduled episode of essential nursing care.

Measures, Aim 3:

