- ***NAPI.*** The NAPI is a neurobehavioral assessment for preterm infants between 32 weeks PMA and term equivalent age ⁹¹. The assessment includes seven "clusters" – motor development and vigor, scarf sign, popliteal angle, alertness and orientation, percent asleep ratings, irritability, and vigor of crying – that, together, define the developmental maturity of the preterm infant ⁹². A recently published systematic review of neonatal assessments concluded that the NAPI had excellent content validity and adequate reliability and construct and criterion validity ⁹³. The NAPI can be used for evaluative or discriminative purposes and has published preterm infant norms ⁹³. The NAPI is able to discriminate between extremely low birthweight and very low birthweight infants and is significantly correlated with neurodevelopmental assessment scores at 18 and 30 months corrected age ⁹⁴. Moreover, previous research found that acute stress and degree of prematurity predicted scores on two clusters of the NAPI ⁹⁵. The NAPI is administered approximately one hour prior to a feeding and in a specified, invariable sequence to minimize the variance in infant responses attributable to inconsistencies in test administration ⁹¹. Co-I [name] has previously used the NAPI in her studies of preterm infants⁷⁴.

6.3 ***Infant participants.*** To protect the privacy of infants and their parents, we will meet with bedside caregivers prior to contacting parents to ensure that it is an appropriate time to discuss the study. If parents indicate at any time that they are

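### Should exploratory Aim 3 specify how age at NAPI testing enters the analysis, since testing age moves with the infant's clinical course?

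*Combined protocol and SAP*

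**What the plan says.** Sections 1.0, 2.1 and 6.1 give the formal Aim 3, labelled exploratory in section 2.1: associations between biobehavioral responses and early neurobehavior, with no age in the wording of the aim. The 35-week figure is the scheduled time of the test (sections 1.0, 4.1 and 6.2). It also appears once in Background, section 3.1: "Thus, we will determine associations between HRV, as well as HR, SCRs, and cortisol, and infant neurobehavior at 35 weeks PMA".

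Section 4.1 says openly that timing is flexible: "The timing of this assessment will depend on anticipated discharge and clinical stability". Section 6.2 (Procedures, Aim 3) brings the test forward when discharge is expected before 35 weeks. For infants who are unstable, invasively ventilated or on CPAP, "we will delay the neurobehavioral assessment until the infant is clinically stable", with no latest date.

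On the instrument, section 6.2 (Measures, Aim 3) states: "The NAPI is a neurobehavioral assessment for preterm infants between 32 weeks PMA and term equivalent age". It adds that the seven clusters together describe developmental maturity and that preterm norms have been published.

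The Aim 3 analysis in section 17.1 is one sentence naming correlation analysis and regression models. The clause on adding confounders, and PMA at birth as a moderator, both belong to Aim 1.

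**The concern.** A maturity score taken at 38 weeks is not on the same footing as one taken at 34 weeks. If sicker infants are tested later and healthier ones earlier, testing age is tied to illness. If illness is also tied to the stress response, a plain correlation of stress response with NAPI score partly reflects when each infant could be tested. An association could be masked, exaggerated or, in the extreme, created.

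Nothing in the plan bounds the testing age. The participation length looks as if it might, since section 4.1 says "Infant participation for the entire study will last between 5-7 weeks, depending on infant PMA at birth and timing of the neurobehavioral assessment" and section 1.0 counts it from the first observation, but it is approximate and does not act as a uniform limit (see the working).

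At stake is the interpretation of Aim 3 estimates for a later study; section 3.1 suggests HRV might serve as an endpoint for powering one. Aim 1 does not use the NAPI.

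**Working it through.** The documents give no effect size, SD, alpha or power for Aim 3, so there is no stated figure to reproduce. The check has four parts.

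**1. Does the 5-7 weeks cap testing age?** Section 6.2 says "data collection for stress responses will occur between 10 and 20 days of life". Seven weeks (49 days) after first observation is:
- born 27w0d, observed day 10: 27w0d + 59 days = 35w3d
- born 30w0d, observed day 20: 30w0d + 69 days = 39w6d

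So it is not a common cap, and testing age can vary as the concern says.

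**2. How far could testing age alone move an estimate?** All inputs here are assumptions: true standardised slope -0.30; stress-illness correlation r = -0.4, 0 or +0.4; NAPI gain g = 0.2 to 0.4 SD per week; sickest 20% tested 0.5-3 weeks late (mean 1.75); healthiest 20% tested 0-1 week early (mean 0.5).

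With illness standard normal, the covariance of illness and testing age is c = 0.280 × 1.75 + 0.280 × 0.5 = 0.63, where 0.280 is the normal density at the 80th percentile. The error in the unadjusted slope is r × g × c:
- g = 0.2: 0.4 × 0.2 × 0.63 = 0.05
- g = 0.4: 0.4 × 0.4 × 0.63 = 0.10
- r = 0: no error; r = -0.4: same size, opposite sign

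With 10% tested late (0.5-2 weeks, mean 1.25) and 2% early (mean 0.25), c = 0.1755 × 1.25 + 0.0484 × 0.25 = 0.23, and the error is 0.02 to 0.04.

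**3. Does adjusting for testing age bring the estimate closer?** Let illness also change the NAPI score directly by d SD. The errors are then:
- unadjusted: r(0.63g + d)
- age-adjusted: d × r(1 - ρ²)/(1 - r²ρ²), where ρ = 0.74 is the correlation of illness with testing age. At r = 0.4 this is d × 0.4 × 0.450/0.912 = 0.197d.

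Absolute errors at r = +0.4 (the same at r = -0.4, with signs reversed):

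| | d = -0.1 | d = -0.2 | d = -0.3 | d = -0.5 |
|---|---|---|---|---|
| Unadjusted, g = 0.2 | 0.010 | 0.030 | 0.070 | 0.150 |
| Unadjusted, g = 0.3 | 0.036 | 0.004 | 0.044 | 0.124 |
| Unadjusted, g = 0.4 | 0.061 | 0.021 | 0.019 | 0.099 |
| Age-adjusted, any g | 0.020 | 0.039 | 0.059 | 0.099 |

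Of the 12 comparisons, adjustment is farther from the truth in 6, closer in 5 and level in 1 (g = 0.4, d = -0.5). Being tested later raises the score while illness lowers it, so in the unadjusted slope the two partly cancel. Adjusting for age removes one and leaves the other. Adjustment is right throughout only when d = 0.

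**4. Scale against sampling error.** Fisher's z for r = -0.30: atanh(-0.30) = -0.310, with standard error 1/√(16 - 3) = 0.277. The 95% limits on the z scale are -0.853 and +0.234, which convert to -0.69 and +0.23. With one covariate the standard error is 1/√12 = 0.289, giving -0.70 to +0.25. The largest shift in part 2 (0.10) is about a ninth of the interval's width (0.23 + 0.69 = 0.92).

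**The case for a change.** The best case for a change is that the omission is real and cheap to repair. Section 1.0 as well as Background puts the assessment at 35 weeks. Leaving the choice until the data are in allows raw, adjusted or norm-referenced results to be favoured after the fact. One covariate costs one degree of freedom, needs no extra visit, and widens the interval only slightly. When testing age is related to both stress response and score and illness has no direct effect, the unadjusted test misleads: with assumed age-stress correlations of 0.2 to 0.6 and age-NAPI correlations of 0.3 to 0.7, a two-sided 5% test at n = 16 rejects a true null 5.7% to 38% of the time, against about 5% after adjustment.

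Part of this stands. The plan is silent, and a careful report should give PMA at NAPI and the reason for each off-schedule test. The rest is weaker:
- The 38% figure needs correlations of 0.6 and 0.7. The timing model above implies an age-stress correlation of about 0.4 × 0.74 = 0.30.
- The figure also assumes no direct illness effect, which is doubtful when illness is what delays the test.
- Aim 3 states no alpha or decision rule, so there is no error rate to protect.
- Giving every estimate in two forms takes 4 stress measures × 7 clusters = 28 pairs to 56 estimates on 16 infants, without telling the reader which form is nearer the truth.

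**Conclusion.** No change follows. This is an unspecified detail in an exploratory aim of a pilot. It is not an analysis error, and no bias of known size or direction has been shown. The plan already permits the sensible course: regression is named, PMA is recorded (section 6.2, Demographic and clinical data), norms are cited, and a statistical co-investigator conducts the analysis (section 25.2). Flexible timing is a disclosed trade-off for testing infants who may go home early or may not yet be stable.

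Under the assumptions above, the effect of testing age alone is 0 to 0.10 on a standardised slope, and 0.02 to 0.04 if few infants are off schedule. A fixed age adjustment is not clearly an improvement, since it did worse about as often as better once illness affected the score directly. SNAP-II would not settle this, because it covers only the first 12 hours of life.

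The conclusion depends on the aim staying exploratory with about 16 usable infants. The off-schedule rate, NAPI gain per week and illness effect are all assumed. A confirmatory use of these associations, or a large share of very late tests, would reopen the question.

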7.0 Data and Specimen Banking*

7.1 With parental consent for infant data and nurse consent for nurse data, all data will be stored indefinitely on the OSU CON's secure research server or in locked filing cabinets within a locked office in the OSU CON. After the required data retention period, the encrypted key linking SIDs with participant identities will be deleted. The resulting dataset will contain only de-identified data. We will not store samples collected during this study long-term. There will be no samples remaining after this study is complete.

7.2 Data may be used for future unspecified research with parental and nurse consent, which will be provided with the initial consent for this study. Future studies will be related to this research and will undergo IRB review prior to the use of any data collected during this study, as required. Data will not be available for use outside of this research team.

8.0 Sharing of Results with Subjects*

8.1 Individual results will not be shared with participants. If parents are present at the time of the neurobehavioral assessment, we will explain the range of responses possible for preterm infants and will describe mature versus immature responses. Parents of participating infants and nurse participants may request aggregate data to be distributed at the conclusion of the study by writing to [name], [name]. Study results will also be disseminated through peer-reviewed publications and internal and external research presentations.

9.0 Study Timelines*

9.1 Participation for infants each day will last approximately 6 hours and will begin when electrodes to measure SCRs are attached to the infant during the care episode prior to the observed care. Infant participation to measure biobehavioral responses to care will last approximately 24-48 hours and will include two 6-hour observation periods as described above, one each on two consecutive days. If a participating infant is not available on the second consecutive day due to an off-unit or scheduled procedure, data collection will resume on the next possible day. Total infant participation in the study will last between 5-7 weeks, depending on PMA at birth and the timing of the neurobehavioral assessment planned for 35 weeks PMA. Nurse participation is expected to last 15-20 minutes or the time required to complete the demographic questionnaire and study questionnaires. Nurses may be asked to complete additional sets of questionnaires if they provide the NaTI more than once.

We expect that infant enrollment will require four months. Nurse participants will be enrolled at the time of infant data collection for infants.

Preliminary data analysis should be complete 9 months after enrollment of the first infant participant.

10.0 Inclusion and Exclusion Criteria*

10.1 ***Infant participants.*** We will request a partial HIPAA waiver for activities preparatory to research to periodically screen the NICU census for eligible infants. We will first screen the census to identify infants born in the specified age range (i.e. 27-30 PMA). Infants who are eligible by PMA at birth will be further screened for eligibility based on inclusion and exclusion criteria.

Nurse participants. Eligible nurse participants will be identified by the research team during infant data collection as those caring for infants receiving the NaTI. No screening of nurse participants will be required.

10.2 ***Infant participants.*** Infants will be included if they are (1) born between 27-30 weeks PMA, (2) born to mothers who are English-speaking and able to provide informed consent, and (3) no more than 10 days old at the time of enrollment. Infants will be excluded if they (1) are diagnosed with Grade III/IV intraventricular hemorrhage or other neurologic abnormality (e.g. seizure disorder) affecting sensory perception or motor function, (2) are diagnosed with a congenital anomaly requiring surgery during the neonatal period, (3) are receiving scheduled steroids or vasoconstrictors, (4) have skin conditions that preclude the attachment of sensors, (5)

are diagnosed with neonatal abstinence syndrome or born to mothers with known illicit drug use, except marijuana, during pregnancy, (6) are diagnosed with chromosomal abnormalities, or (7) require special isolation that includes universal gloving for potentially infectious pathogens.

Nurse participants. Eligible nurses will be those providing care to infants receiving the NaTI. There are no additional inclusion or exclusion criteria for nurses.

10.3 **Infant participants.** All infant participants will be preterm infants.

Nurse participants. Nurse participants will be nurses working in the NICU. There may be pregnant nurses in the sample of nurse participants.

11.0 **Vulnerable Populations***

11.1 **Infant participants.** Participants in this study will be preterm infants born 27-30 weeks PMA. We will not enroll extremely preterm infants of uncertain viability. The study procedures pose no more than minimal risk to infant participants and may have potential, if slight, benefit for infants. We will obtain written informed consent from parents prior to the initiation of any study procedures. Parents will be given adequate time to consider participation in the study prior to providing written informed consent. Infant participants will not provide assent, as infants are developmentally unable to do so.

Nurse participants. Nurse participants may include pregnant women. This is a minimal risk study for nurse participants and poses no physical risk to a pregnant nurse's fetus. Nurse participants will provide written informed consent prior to participation.

12.0 **Local Number of Subjects**

12.1 **Infant participants.** All infants will be enrolled from the NCH NICUs. We will enroll up to 20 infants to collect complete, usable data from 16 infants.

Nurse participants. Nurses will be those employed in the NCH NICUs. We will invite all nurses who provide care to infants receiving the NaTI to participate in the survey study, providing up to 20 total opportunities for nurse responses. Assuming 80% participation, we expect up to 16 nurse responses.

13.0 **Recruitment Methods**

13.1 **Infant participants.** After identifying an eligible infant, study staff will meet with parents in the NICU or in the mother's postpartum hospital room to introduce the study. Study staff will wait until parents have visited the NICU to see their infant and receive a medical update prior to attempting to contact parents. Study staff will check with bedside caregivers in the NICU or the postpartum unit to ensure that it is an appropriate time to meet with parents. During the first meeting, study staff will provide parents with an informational flier that outlines the study purpose and procedures. We will ask parents if it is a good time to discuss their infant's eligibility for a research study and will conduct any follow-up discussion either in person or over the phone based on parental preference. Study staff will provide a thorough overview of the study, including the study purpose, procedures, potential

PROTOCOL TITLE: Pilot Study of Nurse-Administered Touch and Biobehavioral Stress Responses of Preterm Infants (Pilot NAT-BIO Study)

risks and benefits, and the voluntary nature of participation and will inform parents that they may withdraw from the study at any time. Parents will have until their infant reaches two weeks of age to decide whether or not to participate in the study. For this minimal risk study, written informed consent will be required from one parent. If parents are unmarried without a paternity affidavit, consent will be obtained from the mother according to Ohio law.

Nurse participants. Prior to beginning infant enrollment, we will provide unit-based education for staff to introduce the intervention and the nursing survey study. Nurses will be individually approached at the time of infant observation. Study staff will provide an overview of the nursing survey study, including a discussion of the study purpose, surveys, potential risks, and the voluntary nature of the study. Nurses will have until the end of their shift to decide whether or not to participate in the study. At the time that consent is obtained, we will explain to nurses that they may be asked to complete additional surveys if they provide the NaTI again. They will be told at the time of consent and reminded, if they are asked to complete additional surveys, that study participation is completely voluntary. Study staff will further inform nurses that their decision to participate in the study will have no effect on their employment.

- 13.2 All infant participants will be hospitalized patients in the NCH NICUs. Nurse participants will be registered or licensed practical nurses employed in the NCH NICUs and providing care to infants receiving the NaTI.
- 13.3 Potential infant participants will be identified through periodic screening of the NICU census for recently admitted infants who meet inclusion criteria. Potential nurse participants will be identified during data collection for infants.
- 13.4 We will provide nurses employed in the NCH NICUs with an educational PowerPoint prior to the enrollment of infants. This PowerPoint will provide an overview of the study and will introduce nurses to the nursing survey study.
- 13.5 We will provide a small board book to participating infants at the time of the first observation and data collection. We will provide nurses with a \$10 Target gift card at the time of data collection each time they agree to complete a set of surveys.

